7.6. Medical History and Surgical History

All adverse events (AEs) and surgical history that occurred prior to the first dose of study medication in Stage 1 (ie, before Stage 1 Period 1) will be considered as medical history. Medical history will be summarized on the All Enrolled Subjects population based on the methodology described in Section 6.2.1 and presented as outlined in Section 6.2.2.1. There will be no separate summaries for each stage of the study.

Past IARs and medical and surgical history will be coded using the Medical Dictionary for Regulatory Activities (MedDRA) 23.0 into system organ class (SOC) and preferred term (PT). Medical history will then be summarized by SOC and by PT within each SOC for the Safety population, with both the SOCs and the PTs within the SOCs sorted by decreasing frequency in the total column. A listing of medical history will be provided and will include the investigator verbatim as well as the PTs and SOCs. Past IARs will be presented in a similar fashion but will be summarized by SOC, PT, and severity.

Note: Medical and surgical history summaries and listings were previously reported in iCSR-1 and will not be repeated in this SAP unless there has been a change in the underlying data. If there has been a change in the underlying data, then the changes in medical history will be identified in the data listings. Otherwise, for the final CSR, the plan is to copy the pertinent summaries from iCSR-1.

7.7. Prior and Concomitant Medications and Non-drug Therapies

Prior medications and non-drug therapies are defined as medications and non-drug therapies taken or occurring prior to the first dose of the study medication. These will be summarized 2 ways, as follows:

- Prior medications and non-drug therapies that were taken or occurring prior to the first dose of study medication (before Stage 1 Period 1). Note: These were reported in iCSR-1 and will not be repeated in this SAP, as the results are not expected to change.
- Prior medications and non-drug therapies that were taken or occurring prior to the first dose of the 20 mg/kg ATB200 + 260 mg AT2221 study medication (in Stage 2 Period 5, Visit 9).

Concomitant medications and non-drug therapies include medications with onset dates on or after the first dose of study medication, medications with onset dates prior to the first dose of study medication without a stop date, or medications with a stop date after the first dose of study medication. A single medication or therapy may be both concomitant and prior. These will be summarized by study stage, as follows:

- For Stage 1: Concomitant medications and non-drug therapies with onset dates on or after the first dose of study medication Stage 1, which will be presented by the SAD treatment dose
- For Stage 2: Concomitant medications and non-drug therapies with onset dates on or after the first dose of study medication Stage 2, which will be presented by the MAD treatment dose
- For Stages 3 and 4: Concomitant medications and non-drug therapies with onset dates on or after the first dose of the 20 mg/kg ATB200 + 260 mg AT2221 study medication (in Stage 2 Period 5)

Prior and concomitant medications and non-drug therapies will be coded to indication-specific Anatomical Therapeutic Chemical (ATC) classification and preferred name using the World Health Organization Drug Dictionary (WHODD, 01 MARCH 2020 DDE B3) and then summarized by level 4 ATC and preferred name using number and percentage of subjects on the Safety population. The summary will be based on the methodology described in Section [6.2.1](#) and presented as outlined in Section [6.2.2.3](#).

Medications and non-drug therapies will be sorted alphabetically by ATC and preferred name within ATC. Subjects with multiple occurrences of a medication in ATC and preferred name will only be counted once within each ATC and preferred name. Because medications are coded to ATC by indication, preferred names may appear under multiple ATCs.

A listing of all medications, both prior and concomitant, will be presented. Any abbreviations and codes will be clearly explained on each page of the listing. The listing will be sorted by cohort (and/or treatment dose) and subject identifier and will include level 4 ATC name, preferred name, reported medication name, dose, route of administration, dosing frequency, start date/study day, end date/study day, indication, and period of medication (prior only, concomitant only, prior and concomitant). Investigator verbatim as well as coded terms will be included in the listings. Non-drug therapies will be similarly listed.

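### SAP 7.7 counts items already in use as concomitant, but its Stage 3–4 bullet tabulates only those started on or after the first 20 mg/kg ATB200 + 260 mg AT2221 dose

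*SAP*

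**What the plan says.** SAP Section 7.7 gives the definition first: "Concomitant medications and non-drug therapies include medications with onset dates on or after the first dose of study medication". It then extends the category to two kinds of earlier item, namely "medications with onset dates prior to the first dose of study medication without a stop date, or medications with a stop date after" that dose. It adds: "A single medication or therapy may be both concomitant and prior". The link from definition to tables is the sentence "These will be summarized by study stage, as follows".

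Three bullets follow:
- Stage 1: "Concomitant medications and non-drug therapies with onset dates on or after the first dose of study medication Stage 1".
- Stage 2: "Concomitant medications and non-drug therapies with onset dates on or after the first dose of study medication Stage 2".
- Stages 3 and 4 combined: "Concomitant medications and non-drug therapies with onset dates on or after the first dose of the 20 mg/kg ATB200" given with 260 mg AT2221, with a parenthesis placing that dose in Stage 2 Period 5.

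The same section plans a prior-medication summary of whatever was taken or occurring before that same dose. It also plans a listing of all medications with start and end dates and a flag for prior only, concomitant only, or both. Non-drug therapies are to be listed in the same way.

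**The concern.** The definition has three routes into the concomitant category, and each bullet keeps only the first. A drug or therapy already under way at the first 20 mg/kg + 260 mg dose and continued afterwards is concomitant by the definition, yet absent from the table meant to describe concomitant use in that period.

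The items concerned matter for reading the results. Protocol Section 10.2.5 requires physiotherapy and occupational therapy to be recorded, and Section 8.6 names physical therapy and assistive devices as nondrug therapies. Section 8.7 provides for some subjects to remain on a non-selective β-blocker that they were already taking. The study is open-label and descriptive, with no covariate adjustment (SAP 9.3) and no subgroups other than cohort (SAP 9.8). The medication tables are therefore the main aggregate view of other treatment during efficacy follow-up.

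Cohort 1 adds a complication. Its efficacy baseline is Visit 2 (SAP 6.4.1), but the reference dose for the Stage 3–4 table is at Visit 9, Day 85 (SAP 6.4.5). Physiotherapy begun on, say, Day 30 and continued starts after the efficacy baseline and could bear on change in walking distance, yet the Stage 3–4 table would not show it.

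**Working it through.** The plan states no figure to reproduce. The check applies the definition and the Stage 3–4 bullet to each pattern of start and stop dates. Let D be the first dose of 20 mg/kg ATB200 + 260 mg AT2221.

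| Start | Stop | Concomitant by the definition, relative to D? | In the Stage 3–4 table by the bullet? |
|---|---|---|---|
| On or after D | Any | Yes | Yes |
| Before D | None recorded | Yes | No |
| Before D | After D | Yes | No |
| Before D | Before D | No (prior only) | No |

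Two of the three defined routes are filtered out.

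The definition refers only to the first dose of study medication. For Cohort 1 that could mean the first Stage 1 dose, D0, which precedes D. The result is the same. An item that started between D0 and D enters by the first route. An item that started before D0 and has no stop date, or a stop date after D, enters by the second or third. Either way it is concomitant by the definition and excluded by the bullet.

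Other parts of the SAP fit the definition better than the bullets:
- With D as reference, no item in the Stage 3–4 table can be both prior and concomitant, although 7.7 says that an item may be both and the listing carries a flag for it.
- SAP 10.1.2 sets out nine steps for incomplete medication stop dates. Under the bullets, stop dates play no part in who enters the table.
- SAP 7.8 gives pre-infusion medications a row for subjects who continued a prior one. Section 7.7 has no such row.
- Protocol 12.4.4.3 asks only for prior and concomitant medications to be summarized by cohort. The table of changes in SAP Section 11 lists no restriction by onset.

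On size, let f be the share of a therapy's Stage 3–4 users whose only records of it began before D. The table then shows a fraction 1 − f of those users. The documents give no f for any therapy, so the identity only bounds the reported share between none and all.

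**The case against.** Three counter-arguments carry weight.

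First, a reader might infer that long-standing drugs and therapies disappear from the report. They do not. Everything begun before D is in the prior-medication summary anchored to D, and everything is in the dated, flagged listing. Cohort 1 items begun in Stage 1 or Stage 2 also meet the onset condition of at least one of those stages' bullets. What remains is narrower: the prior summary mixes stopped with ongoing items, so actual Stage 3–4 use cannot be read from any table.

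Second, the bullets may be loose drafting, meant only to reset the reference dose by stage. Each opens with the term just defined. That is plausible, but the SAP does not say so, and a programmer following the text would apply the onset filter. Two programmers could produce different tables.

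Third, the consequence is limited. There is no inference (SAP 6.2.1), no efficacy analysis uses the table, and counts by drug class would not tie a therapy to one subject's change in function even if complete. With 18 to 34 subjects planned, the listing can serve for that. This argument stands, and it keeps the point descriptive.

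A reader might also set f between 0.5 and 0.9 and conclude that the table shows only 50% to 10% of true users. Those figures would simply restate the assumption, because nothing in the documents supports a value of f. In addition, the start-date imputation in SAP 10.1.1 can move some incomplete dates to the first application of study drug. The loss is therefore certain only for items with a known earlier start.

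**Conclusion.** Section 7.7 contradicts itself. Followed as written, the Stage 3–4 concomitant table under-counts use during the efficacy and long-term safety period, because it omits ongoing items that the section's own definition includes. This rests on the bullet being programmed literally and on the earlier start dates being known. The size of the under-count is not computable from the documents.

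The effect is confined to one descriptive table. The documents do not support reading it as a bias in any efficacy or safety estimate. Nor do they show that the Stage 1–2 tables already reported are wrong: the bullets for those stages share the wording, but the documents do not show which rule was actually programmed for the first interim report. The point is worth correcting because the definition and the table rule cannot both be followed and the change is small.

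**What to change.** Reword the Stages 3 and 4 bullet to apply all three routes relative to the first 20 mg/kg ATB200 + 260 mg AT2221 dose: onset on or after that dose, or earlier onset with either no stop date or a stop date after it. Add a row for items newly started on or after that dose, so that new use stays visible.

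Leave the Stage 1–2 tables alone. SAP 6.2.2.3 plans to copy those summaries from the first interim report unless the underlying data change. Add a footnote stating which rule they used. If they are rerun, apply the same definition, bounded by the end of each stage. The present Stage 1 and Stage 2 bullets have no upper bound, so an item begun in Stage 4 would literally qualify for the Stage 1 table.

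The cost is one wording change and one date condition in the program, plus the added row and the footnote. The Stage 3–4 percentages will rise wherever items were ongoing at the reference dose and may not match the earlier interim report, which the footnote should say.

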7.8. Prior and Concomitant Pre-infusion Medications

Pre-infusion medications are medications administered to subjects prior to infusion with ATB200 to prevent IARs. Both prior pre-infusion medication (taken before the first dose of cipaglucosidase alfa IV infusion study drug) as well as concomitant pre-infusion medications taken during the study (ie, those that start on or after the first dose of study drug but before the last dose of study drug) will be summarized cumulatively by cohort (including total) for the Safety population.

For the prior pre-infusion medication summary, the presentation will include a row for the number (n) and percentage (%) of subjects who used any prior pre-infusion medications.

For concomitant pre-infusion medications (taken during study), the presentation will include rows for the:

- Number (n) and percentage (%) of subjects who used concomitant pre-infusion medications.
- Number (n) and percentage (%) of subjects who continued with their prior pre-infusion medications.
- Number (n) and percentage (%) of subjects who initiated at least 1 pre-infusion medication during the study (regardless of whether they had received that medication in the past).

A listing of all pre-infusion medications will be provided, and this display will include columns for subject ID, Cohort, ATC Level 4/drug name/report name, start date and time relative to original study Day 1, end date and time relative to original study Day 1, and dose (unit)/route/frequency. Flags will be added to this listing to indicate whether the medication was:

- Only used as a prior pre-infusion medication,
- Used as a concomitant pre-infusion medication,
- Used as both prior and concomitant pre-infusion medication, and
- Used as a concomitant pre-infusion medication that was initiated during the study (regardless of whether it had been used in the past) but not as a prior pre-infusion medication that continued on to become a concomitant medication.

8. PHARMACOKINETIC AND IMMUNOGENICITY EVALUATION

8.1. Pharmacokinetic Analysis

This SAP does not cover the evaluation of PK data. Noncompartmental PK-related analyses were described in Section 12.4.4.1 of Protocol ATB200-02, and population PK-related analyses were described in a separate Modeling and Simulation Plan and reported in iCSR-1. These included the noncompartmental analyses, including treatment or population comparisons or dose proportionality assessments of primary PK parameters and population PK analysis from plasma total GAA protein by signature peptides T09 and T50 (as measured by liquid chromatography coupled to tandem mass spectrometry [LC-MS/MS method]) and plasma AT2221 (as measured by LC-MS/MS assay).

No PK samples have been collected in this study since iCSR-1, so the pertinent summaries from the previous iCSR-1 will be copied into the final CSR with reference to the relevant Modeling and Simulation Plan in the CSR.

8.2. Immunogenicity Analysis

This SAP does not cover the evaluation of IMG data. The analysis of IMG data including the evaluation of anti-rhGAA antibodies (total and neutralizing), cross-reactivity of anti-rhGAA antibodies to alglucosidase alfa, pro-inflammatory cytokines, and other biomarkers of immune system activation, as well as the impact of anti-rhGAA antibodies on PK, PD, safety, and efficacy, will be covered in a separate Modeling and Simulation Plan.

9. EFFICACY EVALUATION

9.1. Statement of the Null and Alternative Hypotheses

No hypothesis testing was planned for this study.

9.2. Multiple Comparisons/Multiplicity

No adjustment for multiplicity is planned for this study.

9.3. Adjustments for Covariates/Prognostic Variables

No adjustments for covariates are planned in the statistical analyses.

9.4. Analysis of Efficacy Variables

All efficacy analyses will be conducted on the Efficacy population using the summary statistics defined in Section 6.2.1 and presented as described in Section 6.2.2.4. By-visit summaries will be based on the analysis visit windows defined in Section 6.5, which includes summary at baseline, every 3 months in Stage 3, and every 6 months in Stage 4. All efficacy data will be listed in subject-level data listings. See [Appendix 1](#) for the description of the endpoints as well as the derivation of the % predicted 6MWD, % predicted MIP, % predicted MEP, % predicted SNIP, and the total scores for the FSS, RHS, MMT, R-PAct, GSGC, and the PROMIS scales.

9.4.1. Motor Function Tests

Motor function tests (MFTs) will be summarized for all ambulatory subjects (that is, Cohorts 1, 3, and 4). The time in seconds (s) that the subject takes to accomplish each task (ie, Gowers' maneuver, 10MWT, 4-stair climb, chair test, and TUG) will be summarized. The assigned functional scores, which indicate the level of difficulty with which the subject performed the task, will be analyzed as continuous variables. The actual score, absolute change, and percent change from baseline in the test scores will be summarized.

The GSGC score will be analyzed as a continuous variable. The actual score, absolute change, and percent change from baseline will be summarized.

The 6MWD and % predicted 6MWD will be summarized for the actual value, absolute change, and percent change from baseline value. A listing of the data for each MFT including individual scores and summary scores will be provided.

9.4.2. Muscle Strength Tests

The MMT summary scores will be provided for the following:

- Body part (shoulder, elbow, knee, and hip)
- Proximal muscles (shoulder and hip)
- Body side (lower, upper)
- Total MMT

Ambulatory subjects were expected to perform all muscle tests, while non-ambulatory subjects were to perform only the upper body muscle tests.

The MMT score at each visit is calculated only if the subject has the corresponding test scores for all applicable muscle groups. The MMT scores will be analyzed as continuous variables at each scheduled visit. The actual score and absolute change from baseline in the MMT scores will be summarized. No percent change from baseline analysis will be performed for the MMTs. A listing of the data for all MMT scores (including individual scores and summary scores) will be provided.

The QMTs will be summarized for the body part, proximal muscles, body side, and total. The actual value, absolute change, and percent change from baseline in the QMT values will be presented. A listing of the data for all QMTs including individual scores and summary scores will be provided.

9.4.3. Pulmonary Function Tests

Pulmonary function tests including sitting and supine FVC, percent predicted FVC, MEP, percent predicted MEP, MIP, percent predicted MIP, SNIP, and percent predicted SNIP will be summarized for ambulatory subjects and for non-ambulatory subjects without invasive ventilatory support. The actual (absolute) value, absolute change, and percent change from baseline in each PFT will be summarized at each visit.

Note: For this study, the spirometer's software has already been programmed to display the correct spirometry predicted values for the subject's age at each session. This means, for example, that the sitting % predicted FVC values are already age-adjusted.

A listing of the lower limit of normal (LLN) values for MIP and MEP for each subject at different time points will be provided. This listing will help identify subjects who had values below the LLN but recovered due to treatment, by having increasing MIP and MEP values above the LLN.

9.5. Patient-reported Outcomes

For each PRO instrument including R-PAct scale, RHS, FSS, and PROMIS scales, the total score is obtained by summing up the individual scores. Summaries will be provided at baseline, Visit 12 and every 3 months in Stage 3, and every 6 months in Stage 4. The actual total score, absolute change, and percent change from baseline in the total score at each visit will be summarized at each visit. The PROMIS scale was introduced in the middle of the study and so baseline scores will not be available. A subject listing of each individual PRO will be provided.

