6.4.3. Change from Baseline and Percent Change from Baseline

Analysis of change from baseline will include only subjects who have assessment at both baseline and the post-baseline time point being analyzed. That is:

- Change from baseline is calculated as: Change = post-baseline result – baseline result.
- Percent change from baseline is calculated as: $100 * (\text{Change from baseline} / \text{Baseline result})$.

If either the baseline or the post-baseline result is missing, the change from baseline and the percentage change from baseline are set to missing.

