 - Gowers' maneuver test is based on the subject lying down on the floor, then rising from the floor to get to a standing position. This is scored as: 1 = normal; 2 = butt first maneuver, one hand on floor; 3 = butt first maneuver, two hands on floor; 4 = unilateral hand support on thigh; 5 = bilateral hand support on thighs; 6 = arises only with aid of an object (table, chair, etc); 7 = unable to rise.

- Chair test is based on the subject arising from a sitting position in a chair to a standing position. This is scored as: 1 = normal; 2 = with wide base and/or difficulty but without support; 3 = with support on one thigh; 4 = with support on both thighs; 5 = with support on arms of chair or on a table; 6 = not possible.

GSGC was performed by ambulatory subjects only. The total GSGC score ranges from 4 (normal performance) to 27 (worst performance).

6. Other motor function tests – ambulatory subjects only

For each of these motor function tests, the actual time (in seconds [s]) that the subject takes to perform the test and the assigned score (which indicates the level of difficulty with which the patient performed this task) are recorded for analysis.

- Gowers' maneuver test is based on the patient lying down on the floor, then rising from the floor to get to a standing position. The time is measured in seconds (s) and assigned the test score.
- 10-meter walk test (10MWT) is based on the time it takes the subject to walk 10 meters. The score from this test is used as the Gait score in GSGC.
- 4-stair climb is based on the subject climbing 4 stairs.
- Timed Up and Go (TUG) test represents the time it takes the subject to stand up from the chair, walk to the line on the floor (about 3 meters), turn around, walk back to the chair, and sit down, all at the regular pace.

7. Rasch-built Pompe-specific Activity (R-PAct) consists of 18 questions, each scored on a scale from 0 = 'no,' 1 = 'yes, but with difficulty,' to 2 = 'yes, without difficulty.'

The 'summed raw score' or total score ranges from 0 to 36, with higher values representing lower level of disease impact on the muscles. The total score will be calculated simply by summing up the observed scores across the 18 items. The total score is analyzed as a continuous variable.

8. Rotterdam Handicap Scale (RHS): This consists of 9 questions, each scored on a scale from 1 = 'unable to perform task' to 4 = 'able to perform task independently or completely.'

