The total score ranges from 8 – 40, with higher scores indicating more fatigue.

- PROMIS – Upper Extremity Short Form 7a consists of 7 items each scored on a decreasing scale from 1 to 5 as follows: 1 = unable to do; 2 = with much difficulty; 3 = with some difficulty; 4 = with a little difficulty; 5 = without any difficulty.

The total score ranges from 7 – 35, with higher scores indicating less disability in the upper extremity.

- PROMIS – Dyspnea Severity Short Form 10a consists of 10 questions each scored on a scale from 0 to 3 as follows: 0 = no shortness of breath; 1 = mildly short of breath; 2 = moderately short of breath; 3 = severely short of breath.

The total score ranges from 10 – 50, with higher scores indicating greater shortness of breath.

The total score of each PROMIS instrument is obtained by summing up the individual scores, and it will be analyzed as a continuous variable.

11. Global impression of change

- SGIC: The Subject’s Global Impression of Change involves 8 questions assessing each of the following functional areas:
 - overall physical wellbeing
 - effort of breathing

- muscle strength
- muscle function
- ability to move around
- activities of daily living
- energy level
- level of muscular pain

Each of the 8 functional items is scored on a 7-point rating scale as follows: 1 = very much worse; 2 = much worse; 3 = worse; 4 = no change; 5 = improved; 6 = much improved; 7 = very much improved.

For each functional item, a ternary response is defined as: “Improved” = item response of 5 or higher, ‘No change’ = item response of 4, or “Declining” = item response of 3 or lower.

- PGIC: The Physician’s Global Impression of Change (PGIC) is based on a single question that is scored on a 7-point rating scale, similarly to the SGIC.
A ternary response is created from the responses, defined as: “Improved” = response of 5 or higher, “No change” = response of 4, or “Declining” = response of 3 or lower.

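### R-PAct percent change from baseline is undefined at zero and its mean drifts upward at low scores; the PROMIS Dyspnea range and PROMIS baseline also need correcting

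*SAP*

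**What the plan says.** SAP 9.5 covers R-PAct, RHS, FSS and the PROMIS scales together: "The actual total score, absolute change, and percent change from baseline in the total score at each visit will be summarized at each visit". SAP 4.4 lists change and percent change for the same instruments, and protocol 12.1.2 lists both for FSS, RHS and R-PAct.

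The formula is in SAP 6.4.3 ("Percent change from baseline is calculated as" 100 times the change over the baseline result). Its only exception concerns missing data: "If either the baseline or the post-baseline result is missing, the change from baseline and the percentage change from baseline are set to missing". A baseline of zero is not mentioned.

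SAP Appendix 1 says R-PAct "consists of 18 questions, each scored on a scale from 0" to 2, and gives the "total score ranges from 0 to 36, with higher values representing lower level of disease impact on the muscles". For PROMIS Dyspnea it describes ten items scored 0 to 3, then prints a range of 10 to 50, "with higher scores indicating greater shortness of breath".

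For manual muscle testing, another ordinal sum whose stated range starts at 0, SAP 9.4.2 decides differently: "No percent change from baseline analysis will be performed for the MMTs".

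On PROMIS, SAP 9.5 adds that the scale came in mid-study and that baseline scores will not exist. Protocol 10.2.9 provides a one-time recall of pre-study status for subjects already on treatment, and protocol Table 13 schedules PROMIS at the Cohort 4 Baseline visit.

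**The concern.** A ratio to baseline needs a denominator that cannot be zero and is not small relative to measurement error. R-PAct guarantees neither. Its total is also a plain sum of the answered items, with no proration of the kind SAP Appendix 1 sets for RHS and FSS, so a skipped item lowers the total.

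There are two consequences. A subject with a baseline of 0 has an absolute change but no percent change, so the two rows of one table would rest on different subjects. And where baselines are low, chance rises weigh more than chance falls of the same size, so the mean percent change is positive even if nobody changes.

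Cohort 2 is planned at 4 to 6 subjects and SAP 6.2.2.4 presents it separately, so one low baseline can dominate its mean. The stake is a descriptive row that may suggest improvement the absolute change does not show.

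**Working it through.** **Ranges, from SAP Appendix 1 (items × lowest and highest item score).**
- R-PAct: 18 × (0, 2) = 0 to 36, as stated.
- RHS: 9 × (1, 4) = 9 to 36, as stated. FSS: 9 × (1, 7) = 9 to 63, as stated. Neither can be 0.
- PROMIS Dyspnea: 10 × (0, 3) = 0 to 30. The printed 10 to 50 does not reproduce; it would need items coded 1 to 5.

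**Asymmetry, with no net change.** Two subjects exchange scores:
- 2 and 4: (+100% − 50%) / 2 = +25%.
- 10 and 12: (+20% − 16.7%) / 2 = +1.7%.
- 24 and 26: (+8.3% − 7.7%) / 2 = +0.3%.

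**Size of the drift.** The documents give neither R-PAct baselines nor its visit-to-visit error, so both are assumed. Simulated baseline and follow-up each equal the same true score plus independent normal error (SD 1, 1.5 or 2 points), rounded and limited to 0 to 36. True scores are uniform on the range shown, and zero baselines are excluded.

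| True scores | Mean percent change, error SD 1 / 1.5 / 2 | Baselines equal to 0 |
|---|---|---|
| 1 to 10 | +5 / +9 / +14 | 2% / 4% / 6% |
| 8 to 18 | +0.8 / +1.8 / +3.2 | none |
| 15 to 30 | +0.2 / +0.5 / +0.9 | none |

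A hand check away from zero: the drift is roughly 100 × σ²/μ² for a subject with true score μ and error SD σ, and the average of 1/μ² over a uniform range a to b is 1/(ab). For 8 to 18 with σ = 2 this gives 100 × 4/144 = 2.8; for 15 to 30 it gives 100 × 4/450 = 0.9. Both are close to the table. The approximation fails near zero, so the first row rests on simulation alone.

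In every row the median percent change is 0 and the mean absolute change over all subjects is 0.00 to within 0.01. In the first row, with six subjects, the SD of the cohort mean is about 20, 29 and 38 points, larger than the drift.

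**Could Cohort 2 score that low?** Nine R-PAct items involve walking, stepping, rising or squatting (items 7, 9 to 14, 17 and 18 in protocol Appendix 3). If all nine scored 0, the maximum would be 9 × 2 = 18. A total of 0 would also need every self-care and upper-limb item to score 0.

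**The case against.** The case for leaving the row alone is fair. SAP 6.2.1 reports n, median, quartiles and extremes beside the mean, so dropped subjects would be visible and the median would not drift. Actual values, absolute change and a subject listing accompany the row, and no hypothesis test uses it. Percent change in R-PAct is listed in the protocol, and a one-line zero-baseline rule would close the formal gap. SAP 9.4.2 gives no reason for omitting percent change for manual muscle testing, so it sets a precedent but not a principle. All of this stands. It limits the importance of the point but does not make the mean percent change a sound summary, because a zero rule leaves the drift in place.

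Two stronger readings are tempting. A reader might infer that Cohort 2 is a low-scoring cohort whose mean will be biased. The documents do not show this: there is no R-PAct baseline for any cohort, being unable to walk unassisted does not exclude assisted walking or standing, and an activity done with difficulty earns a point. A reader might also carry the zero-denominator argument over to PROMIS Dyspnea. There a low score is the good state, and SAP 9.5 says PROMIS baselines will not be available, so absolute change fails along with percent change. The PROMIS problem is an undefined baseline.

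**Conclusion.** The point holds as a minor improvement. From the documents alone, three things are certain: R-PAct percent change is undefined at a baseline the instrument allows; the PROMIS Dyspnea range contradicts its own item scoring; and the SAP orders PROMIS change from baseline while stating there is no baseline.

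The upward drift of the mean is certain in direction where baselines are low relative to error, but its size rests on assumed scores and error: material for true scores of 1 to 10, small for 8 to 18, negligible for 15 to 30. Whether any cohort falls in the first range is unknown. No test, and no conclusion based on medians or absolute change, is affected. The Dyspnea range is a text error that alters no computed total, since totals are sums of item scores.

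**What to change.** 1. In SAP 4.4 and 9.5, report only the actual value and absolute change for R-PAct, as SAP 9.4.2 does for manual muscle testing.
2. Record the departure from protocol 12.1.2 in SAP Table 11. The manual muscle testing departure is not recorded there either, and the same entry could cover both.
3. In SAP Appendix 1, change the PROMIS Dyspnea range from 10 to 50 to 0 to 30.
4. In SAP 4.4 and 9.5, state which PROMIS baseline, if any, is used: the one-time recall in protocol 10.2.9, the scheduled Cohort 4 baseline in protocol Table 13, or none. Report PROMIS change only for subjects with a baseline so defined, and actual values otherwise.

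The cost is a few lines of SAP text and fewer table rows. The downside is the loss of one descriptive summary that the protocol lists.
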